1.7 Intervention Adherence

Adherence will be defined as completion of PVL.

1.8 Protocol Adherence and Retention

Protocol deviations and visit completion rates (excluding deaths) will be tabulated.

1.9 Baseline Descriptive Statistics

Baseline characteristics will be tabulated and summary statistics appropriate to the distribution will be reported.

1.10 Planned Interim Analyses

There is no formal interim analysis planned for this study. The Data and Safety Monitoring Committee (DSMC) will review safety and outcome data approximately every 6 months while the study is ongoing.

1.11 Subgroup Analyses

Subgroup analyses, i.e., assessments of effect modification, will be conducted to detect factors associated with the primary outcome. These analyses will be considered exploratory.

Subgroup analyses will be conducted using logistic regression. The risk difference for the subgroup factor (estimated with conditional standardization),⁴ 95% confidence interval (estimated with the delta method)⁴, and *P* value will be presented. To aid in interpretation of the risk difference, observed outcome proportions will be reported for each subgroup. Subgroup analyses will use data from eyes that complete the 8-week visit or have MH closure or rescue treatment prior to 8 weeks (i.e., complete case analysis as described in section 1.4).

The primary subgroup analysis will evaluate the effect of ERM presence within 1 mm of the center of the macula at baseline.

Secondary subgroup analyses will include ERM presence at the site of vitreous adhesion, lens status (phakic or pseudophakic), retinoschisis, subretinal fluid within 1 mm of the center of the macula, length of adhesion on OCT (less than or equal to 1500 microns or greater than 1500 microns), and diabetes status (has diabetes or does not have diabetes). Subgroups will be defined by the value at baseline.

There are no data to suggest that the treatment success will vary by sex or race/ethnicity. However, both of these factors will be evaluated in exploratory subgroup analyses as mandated by National Institutes of Health (NIH) guidelines.

Subgroup factors will be analyzed as categorical and continuous or ordinal variables where possible. Secondary and exploratory subgroup analyses will only be conducted if there are at

184 least 10 eyes in each subgroup. The primary subgroup analysis will be conducted regardless of
185 sample size.

186 **1.12 Multiple Testing**

187 There will be no adjustments made for multiple testing because this is a single-arm study without
188 treatment group comparisons. Only $P \leq .05$ will be considered of interest.

189 **1.13 Visit Windows for Analysis**

190 The analysis windows for visits will be defined according to Table 1. If multiple visits fall within
191 the same window, priority will be given to the protocol visit over unspecified visits. If there is no
192 protocol visit in the window, then the visit closest to the target date (but within the analysis
193 window) will be designated as the analysis visit. Visit windows will be filled in the following
194 order to handle visits occurring on the border of two windows: 8 weeks, 24 weeks, 4 weeks, 1
195 week.

196 **Table 1. Analysis Windows**

Visit \pm Protocol Window	Target	Analysis Window
1 week (-4 days to +3 days)	7 days	1 day – 2 weeks (1 – 14 days)
4 (± 1) weeks	28 days	2 – 6 weeks (14 – 42 days)
8 (± 2) weeks	56 days	6 – 18 weeks (42 – 126 days)
24 (± 4) weeks	168 days	18 – 40 weeks (126 – 280 days)

197 **1.14 Missing Data**

198 The strategy for handling missing data generally is included with the description of each
199 analysis. For analyses using multiple imputation, the Markov chain Monte Carlo (MCMC)
200 method with 100 imputations will be used. Where otherwise not specified, only participants with
201 non-missing data will be included in analyses.

202 **1.15 Outliers**

203 To ensure that statistical outliers do not have an undue impact on analyses of continuous
204 outcomes, change in continuous outcomes from baseline will be truncated to ± 3 standard
205 deviations based on the overall mean and standard deviation at 8 weeks. Truncation will occur
206 after imputation, where applicable.

207 **1.16 Model Assumptions.**

208 All model assumptions will be verified. If model assumptions are seriously violated, covariates
209 may be categorized or excluded, and a non-parametric approach, robust method, or
210 transformation may be considered.

211 **1.17 Revisions**

212 Owing to lower than anticipated final sample size, the following key changes were made to the
213 analysis plan after review of study data:

214 • Presence of epiretinal membrane has been removed as a covariate from all imputation
215 and regression models.

216 • Proportion of eyes with central VMT release and vitreopapillary traction (VPT)
217 release without rescue treatment at 24 weeks has been removed from the list of
218 secondary outcomes.

219 In addition, subgroup effects will still be analyzed with logistic regression, but the subgroup
220 effect will be summarized with a risk difference instead of a relative risk.

221 References

222 1. Brown LD, Cai TT, DasGupta A. Interval estimation for a binomial proportion.
223 *Statistical Science*. 2001;16(2):101-117.

224 2. Wilson EB. Probable inference, the law of succession, and statistical inference. *Journal*
225 *of the American Statistical Association*. 1927;22(158):209-212.

226 3. Lott A, Reiter JP. Wilson Confidence Intervals for Binomial Proportions With Multiple

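### The delta-method interval planned for the ERM subgroup (SAP 1.11) falls well short of 95% coverage when the split is uneven and the smaller group has few eyes, and the test behind its P value is not named

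*SAP*

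**What the plan says.** SAP 1.11 fits a logistic regression for each subgroup factor and names no other covariate. It reports a risk difference obtained by conditional standardization, a "95% confidence interval (estimated with the delta method", and a P value whose test is not identified. It adds that "observed outcome proportions will be reported for each subgroup" and labels all subgroup analyses exploratory.

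Secondary and exploratory subgroups are analysed only with at least 10 eyes in each group. The ERM analysis is exempt: "The primary subgroup analysis will be conducted regardless of" sample size. SAP 1.12 makes no multiplicity adjustment and treats P values of .05 or below as the ones of interest.

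Three other places bear on this:

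- The SAP version table and SAP 1.17 say the final sample is smaller than anticipated after early stopping. Protocol 8.3.2 planned 50 eyes.
- SAP 1.16 has a general fallback: if assumptions are seriously violated, covariates "may be categorized or excluded, and a non-parametric approach, robust method, or" a transformation may be considered.
- SAP 1.17 states: "Presence of epiretinal membrane has been removed as a covariate from all imputation" and regression models.

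**The concern.** A delta-method interval for a difference in proportions estimates each group's variance from that group's observed proportion. When a small group is at 0% or 100% closure, its estimated variance is zero, although that group is the main source of uncertainty. The interval is then too narrow and can exclude zero when the data are compatible with no ERM effect.

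ERM is the subgroup most exposed, because it is the only one without a size floor and the sample has shrunk. In such tables the logistic estimate also diverges, so different tests give very different P values. Whether a result passes the threshold in SAP 1.12 then depends on a choice the SAP does not record.

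At stake is how an exploratory ERM finding is read. The primary outcome has its own Wilson interval and is unaffected.

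**Working it through.** **Inputs.** Interval method, level and lack of an ERM floor: SAP 1.11. Threshold .05: SAP 1.12. Closure rates of 50, 70 and 85%: Protocol Table 1. Totals of 25 and 35 eyes, the splits, and equal true closure in both groups are assumptions.

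**The plan's own figures.** The documents give no number for the ERM interval. The related figures are the half widths in Protocol Table 1, which follow from the Wilson formula

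z·√[p(1−p)/n + z²/(4n²)] / (1 + z²/n).

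At p = 0.70 and n = 25, 50, 75 this gives 16.94, 12.32 and 10.16, against 16.9, 12.3 and 10.2 in the table. All nine cells agree. The plan thus already uses score intervals for single proportions.

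**Step 1: the planned interval is the Wald interval.** With one binary factor the logistic model is saturated. In group g, Var(logit p̂) = 1/[n p̂(1−p̂)], and the derivative of p with respect to its logit is p(1−p). The delta method therefore gives Var(p̂) = p̂(1−p̂)/n, and

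SE = √[p̂₁(1−p̂₁)/n₁ + p̂₀(1−p̂₀)/n₀].

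A group at 0% or 100% contributes zero.

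**Step 2: an example, 5/5 versus 22/30** (0/5 versus 8/30 is its mirror image).

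- Difference: 1 − 0.7333 = 0.2667.
- Delta SE: √(0 + 0.7333 × 0.2667/30) = 0.0807. Interval: 0.2667 ± 1.96 × 0.0807, or +10.8 to +42.5 points; z = 3.30, P = 0.001. A logistic model with the delta method fitted to the mirror table gives the same limits and P.
- Score SE at no difference, pooled closure 27/35 = 0.7714: √[0.7714 × 0.2286 × (1/5 + 1/30) × 35/34] = 0.206; z = 0.2667/0.206 = 1.30, P = 0.20. The Miettinen-Nurminen interval is about −20 to +45 points.
- Other tests: likelihood ratio P = 0.09, Fisher P = 0.32. The Wald P for the logistic coefficient is 0.79 after 8 iterations and above 0.999 after 25, because the estimate diverges.
- Scale: at a common closure of 27/35, all five eyes close with probability (27/35)⁵ = 0.27.

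For 5/5 versus 14/20 (mirror 0/5 versus 6/20), the delta interval is +10 to +50 points and Miettinen-Nurminen −18 to +52. P is 0.003 (delta z), 0.08 (likelihood ratio), 0.17 (score) and 0.29 (Fisher).

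**Step 3: exact coverage.** All pairs (x₁, x₀) were enumerated with binomial probabilities at equal closure p, summing the probability of samples whose interval contains zero. The smaller group is at 0% or 100% with probability pⁿ + (1−p)ⁿ; for n = 5, p = 0.7 this is 0.168 + 0.002 = 0.17. Entries are percentages at p = 50/70/85%.

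| Split | Smaller group at 0 or 100% | Delta coverage, all samples | Delta coverage, those samples only |
|---|---|---|---|
| 3 v 22 | 25/37/62 | 75/65/72 | 0/6/57 |
| 3 v 32 | 25/37/62 | 75/63/53 | 0/<1/27 |
| 5 v 20 | 6/17/44 | 90/82/83 | 0/11/65 |
| 5 v 30 | 6/17/44 | 88/80/68 | 0/1/32 |

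In all other samples from these four splits, delta coverage is 94 to 100%, so the failure lies in the extreme cells. For larger smaller-groups, delta coverage is 83 to 92% with 8 eyes (8 v 17, 8 v 27), 88 to 94% with 10 (10 v 15, 10 v 25) and 91 to 95% when nearly balanced (12 v 13, 17 v 18). Miettinen-Nurminen coverage is 94.2 to 97.3% across every split listed.

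**Step 4: effect of the unnamed test.** With 5 v 30 eyes and 70% closure in both groups, rejection at .05 is 19.9% for a z-test on the risk difference, 7.9% for likelihood ratio, 2.0% for Fisher and 1.6% for Wald on the log odds ratio.

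**The case against.** The strongest reply is that the bad case is assumed. Neither document gives the final number of eyes or the ERM split, the large shortfalls come from groups of 3 or 5 eyes, and SAP 2.0 was written after data review, so its authors may have known the split. This stands as a limit on size, not on the defect: a rule that applies at any sample size should work at small ones.

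Equal closure is also one scenario, and Protocol 8.13 cites reports that closure differs with ERM. With unequal rates (again assumed), coverage at 5 v 30 is 87% for 40% v 70% and 89% for 50% v 85%; at 5 v 20 it is 88% for 50% v 85%. That is milder but still below nominal.

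On the P value, the natural reading is a test from the logistic model, and in both worked examples only the risk-difference z-test falls below .05. So an inflated false-positive rate is not established; what remains is that the test is unstated and that the printed interval could contradict the printed P.

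SAP 1.16 could be invoked when the model separates, and the reported proportions would expose an extreme cell. Both help. But the remedy in 1.16 is optional, does not mention separation and names no replacement interval, and showing the proportions does not correct the interval. Analysing the single primary subgroup at any size is a legitimate choice; the absent floor matters only because of the interval used.

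**Conclusion.** The concern holds, as a minor point. For a binary subgroup factor the planned 95% interval is a Wald interval that fails when the smaller group is at 0% or 100% closure. With 3 to 5 eyes in the smaller group and equal closure of 50 to 85%, coverage is 53 to 90%. With a near-balanced split there is little problem. The size rests on the assumed totals, splits and closure rates, so confidence in it is medium; the algebra does not depend on them.

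The consequence is confined to an exploratory analysis. The unnamed test is missing detail. The SAP 1.17 statement about ERM is consistent with 1.11 only if it means adjustment covariates, which is how I read it; on any other reading the two sections conflict.

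**What to change.** In SAP 1.11, for binary subgroup factors, report the risk difference with a Miettinen-Nurminen score 95% interval and the P value from the matching score test, so that the two agree. Keep logistic regression for continuous, ordinal and multi-level nominal factors, and name the likelihood-ratio test for their P value. The 10-eye floor already applies to the nominal ones. In SAP 1.17, say that the ERM bullet refers to adjustment covariates, if that is the intent.

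This takes two sentences in 1.11 and a phrase in 1.17, with standard software and no new data. Because SAP 2.0 already followed review of study data, list it in 1.17 as a further change made after that review.

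There are two costs. Intervals will be wider when a subgroup is at 0% or 100% closure. A factor analysed both as categories and on its continuous scale, such as adhesion length, will carry two methods; on the continuous scale, the delta interval and likelihood-ratio P can still disagree.

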OCT	Optical Coherence Tomography
PVD	Posterior Vitreous Detachment
PVL	Pneumatic Vitreolysis
SADE	Serious Adverse Device Event
SAE	Serious Adverse Event
SD	Standard Deviation
UADE	Unanticipated Adverse Device Effect
VMT	Vitreomacular Traction
VMA	Vitreomacular Adhesion

PROTOCOL SUMMARY

PARTICIPANT AREA	DESCRIPTION
Title	Single-Arm Study Assessing the Effects of Pneumatic Vitreolysis on Macular Hole
Précis	Eyes with vitreomacular traction (VMT) and full-thickness macular hole (MH) will be enrolled into a non-randomized cohort treated with PVL to determine the proportion with VMT release and MH closure and to assess factors associated with success.
Investigational Device	Intraocular gas (C ₃ F ₈) injection
Objectives	To obtain estimates of the proportion of eyes with MH closure of the inner retinal layers for eyes with VMT and full-thickness MHs treated with PVL.
Rationale	Understanding the rates of VMT release and MH closures in eyes with full-thickness MH treated with PVL is of interest. Surgery would result in nearly 100% hole closure and VMT release, making vitrectomy a poor control group choice. Spontaneous resolution of MH is highly unlikely, making an observation arm unnecessary. Therefore, these eyes will be enrolled into a non-randomized cohort treated with PVL to assess the outcomes of treatment.
Study Design	Single-arm study
Number of Sites	Approximately 50 sites
Endpoint	
Primary Outcome: Proportion of eyes with MH closure of the inner retinal layers without rescue treatment at 8 weeks.
 
Key Secondary Outcomes: proportion of eyes with central VMT release without rescue treatment, proportion of eyes with rescue treatment, mean change in visual acuity
 
Key Safety Outcomes: retinal tear, retinal detachment, traumatic cataract, cataract extraction, vitreous hemorrhage, intraocular pressure (IOP) increase, and endophthalmitis.

Population	
Key Inclusion Criteria
 
 • Age \geq 18 years. • Able and willing to avoid high altitude until gas resolution (approximately 6 to 8 weeks) • For phakic patients, able and willing to avoid supine positioning until gas resolution (approximately 6 to 8 weeks) • Able and willing to position face down for at least 50% of the time for at least 4 days post-injection • At least 1 eye with:

PARTICIPANT AREA	DESCRIPTION

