 - 616 ▪ MH closure without central VMT release without rescue treatment
 - 617 ▪ MH closure with central VMT release with rescue treatment
 - 618 ▪ MH closure without central VMT release with rescue treatment
- 619 • Proportion of eyes with central VMT release and vitreopapillary traction release* without
620 rescue treatment through 24 weeks (time-to-event analysis).
- 621 • Mean change in visual acuity letter score from baseline at 8 and 24 weeks.
- 622 • Proportion of eyes with at least 10-letter gain (increase) in visual acuity from baseline at
623 8 and 24 weeks.
- 624 • Proportion of eyes with at least 10-letter loss (decrease) in visual acuity from baseline at
625 8 and 24 weeks.
- 626 • Proportion of eyes receiving rescue treatment before the 8-week visit.
- 627 • Proportion of eyes receiving rescue treatment before the 24-week visit.
 - 628 ○ For purposes of description only, the following will be tabulated without
629 statistical comparison:
 - 630 ▪ Proportion of eyes receiving rescue treatment before the 24-week visit or
631 for which rescue treatment is planned at the 24-week visit and medical
632 records confirm rescue treatment occurred within the subsequent 12
633 weeks.
 - 634 ▪ Type of rescue treatment.

635 Exploratory Outcomes:

- 636 • Proportion of eyes with MH closure of the inner retinal layers with outer retinal lucency*
637 without rescue treatment at 8 and 24 weeks.²⁸
- 638 • Proportion of eyes with ellipsoid zone* integrity at 8 and 24 weeks.

639 *Determined by masked grader at the central reading center.

640 To ensure that statistical outliers do not have undue impact on analyses of continuous outcomes,
641 change in continuous outcomes from baseline will be truncated to ± 3 standard deviations based
642 on the overall mean and standard deviation at 8 weeks.

643 **8.5 Analysis Cohorts**

- 644 • Intention-To-Treat (ITT) Analysis Cohort: all enrolled participants irrespective of
645 treatment received.
- 646 • Safety Analysis Cohort: all enrolled participants irrespective of treatment received.
- 647 • Per Protocol Analysis Cohort: only participants that complete the initial treatment (PVL)
648 and do not receive any non-protocol treatments during follow up. Vitrectomy performed
649 according to the criteria in section 4.2.1 is considered per-protocol and will be included in
650 this analysis.

651 The primary analysis will follow the ITT principle and include all enrolled participants.

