652 A per-protocol analysis will be performed to provide additional information regarding the
653 magnitude of the treatment effect. The per-protocol analysis will only be performed if at least
654 10% of enrolled participants would be excluded by these criteria (e.g., 5 or more participants if
655 exactly 50 are enrolled).
656 The ITT analysis is considered the primary analysis. If the results of the per-protocol and ITT
657 analyses give inconsistent results, the per-protocol analysis will be interpreted with caution. In
658 this scenario, exploratory analyses will be performed to evaluate possible factors contributing to
659 the difference.

660 **8.6 Analysis of the Primary Outcome**

661 The primary outcome of MH closure of the inner retinal layers without rescue treatment through
662 8 weeks is a binary variable that is graded by the central reading center. The proportion of eyes
663 meeting the primary outcome will be determined and the 95% Wilson (Score) confidence
664 interval will be calculated.

665 Since the chance of re-opening after closure before 8 or 24 weeks is highly unlikely, an eye with
666 MH closure of the inner retinal layers without rescue treatment at any time prior to 24 weeks will
667 be considered to have met the outcome through 24 weeks if the patient is lost to follow-up.
668 Similarly, any eye receiving rescue treatment prior to 24 weeks will be considered not to have
669 met the outcome through 24 weeks because rescue treatment has been given.

670 Multiple imputation will be used to impute missing data for eyes lost to follow-up that did not
671 have prior MH closure or rescue treatment documented. The imputation model will include
672 presence of ERM within 1 mm of the center of the macula at baseline and MH status at 1, 4, 8,
673 and 24 weeks.

674 A sensitivity analysis will be conducted using the same approach as above but without multiple
675 imputation (i.e., complete-case analysis).

676 **8.7 Analysis of the Secondary and Exploratory Outcomes**

677 The ITT analysis cohort will be used for all secondary and exploratory outcomes.

678 **8.7.1 Secondary Efficacy Outcomes**

679 Macular hole closure of the inner retinal layers without rescue treatment through 24 weeks is a
680 time-to-event outcome. A Kaplan-Meier curve will be constructed and the cumulative probability
681 with 95% confidence interval will be estimated for the final time point. Data from eyes not

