682 observed to have closure or that receive rescue treatment will be censored on the date of their
683 final visit.

684 Central VMT release without rescue treatment and central VMT release with vitreopapillary
685 traction release without rescue treatment through 24 weeks are time-to-event outcomes graded by
686 the central reading center and will be analyzed as above. The latter analysis will be adjusted for
687 vitreopapillary traction status at baseline.

688 Change in visual acuity letter score from baseline at 8 and 24 weeks is a continuous outcome.
689 The mean and 95% confidence interval will be calculated for each time point. Missing data will
690 be imputed with multiple imputation. The imputation model will include presence of ERM
691 within 1 mm of the center of the macula at baseline, baseline visual acuity, change in visual
692 acuity from baseline at 1, 4, 8 and 24 weeks, and MH status at 1, 4, 8, and 24 weeks.

693 The proportion of eyes with at least 10-letter gain (increase) or loss (decrease) in visual acuity
694 from baseline at 8 and 24 weeks are binary variables. Wilson (Score) 95% confidence intervals
695 will be calculated for each time point. The imputed data sets described above for the mean
696 change in visual acuity from baseline will be utilized.

697 The proportion of eyes receiving rescue treatment before 8 and 24 weeks is a binary variable.
698 Wilson (Score) 95% confidence intervals will be calculated for each time point. Complete-case
699 analysis (no imputation of missing data) will be used for this outcome.

700 **8.7.2 Exploratory Efficacy Outcomes**

701 The proportion of eyes with MH closure of the inner retinal layers with outer retinal lucency at 8
702 and 24 weeks is a binary variable graded by the central reading center. Wilson (Score) 95%
703 confidence intervals will be calculated for each time point. Complete-case analysis (no
704 imputation of missing data) will be used for this outcome.

705 The proportion of eyes with ellipsoid zone integrity at 8 and 24 weeks is a binary variable graded
706 by the central reading center (loss of integrity and no loss of integrity). Wilson (Score) 95%
707 confidence intervals will be calculated for each time point. Complete-case analysis (no
708 imputation of missing data) will be used for this outcome.

709 **8.8 Safety Analyses**

710 All reportable adverse events will be categorized as study eye or systemic. All events will be

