Statistical Analysis Plan

DRCR Retina Network Protocol AH: Single-Arm Study Assessing the Effects of Pneumatic Vitreolysis on Macular Hole

ClinicalTrials.gov Identifier: NCT03677869

Version Number	Author	Approver	Effective Date	Revision Description
1.0	[name]	[name]	09 Oct 2019	Initial SAP for Protocol version 2.0
2.0	[name]	[name]	19 Jan 2021	Revisions were made to accommodate a smaller than anticipated sample size after early stopping for safety concerns. Changes were made following review of study data. Details are provided in subsection 1.17. Applies to Protocol version 3.0.

SIGNATURES	
AUTHOR	
APPROVER	

1 **1.0 Overview**

2 The DRCR Retina Network Protocol AH study will evaluate the effectiveness of pneumatic
3 vitreolysis (PVL) in treating eyes with vitreomacular traction (VMT) and full-thickness macular
4 hole (MH). Presence of MH will be graded on optical coherence tomography (OCT) by a reading
5 center prior to enrollment and during follow-up. The primary outcome is at 8 weeks and follow-
6 up continues through 24 weeks.

7 **1.1 Statistical Hypotheses**

8 There are no formal statistical hypotheses that will be evaluated because this is a single-arm
9 study.

10 **1.2 Outcome Measures**

11 For the outcomes below, rescue treatment includes vitrectomy, ocriplasmin, or additional
12 pneumatic vitreolysis during the course of the study.

13 **1.2.1 Primary Efficacy Outcome:**

- 14 • Proportion of eyes with MH closure of the inner retinal layers* without rescue treatment
15 at 8 weeks.
 - 16 ○ For purposes of description only, the distribution of eyes by the following
17 categories at 8 weeks will be tabulated without statistical comparison:
 - 18 ▪ MH closure without rescue treatment
 - 19 ▪ MH closure with rescue treatment
 - 20 ▪ No MH closure and no rescue treatment
 - 21 ▪ No MH closure despite rescue treatment

22 **1.2.2 Secondary Efficacy Outcomes:**

- 23 • Proportion of eyes with MH closure of the inner retinal layers* without rescue treatment
24 through 24 weeks (time-to-event analysis).
- 25 • Proportion of eyes with central VMT release* without rescue treatment through 24 weeks
26 (time-to-event analysis).
 - 27 ○ For purposes of description only, the following will be tabulated without
28 statistical comparison at 8 weeks and 24 weeks:
 - 29 ▪ MH closure with central VMT release without rescue treatment
 - 30 ▪ MH closure without central VMT release without rescue treatment

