67 The ITT analysis is considered the primary analysis. If the results of the per-protocol and ITT
68 analyses give inconsistent results, then the per-protocol analysis will be interpreted with caution.
69 In this scenario, exploratory analyses will be performed to evaluate possible factors contributing
70 to the difference.

71 **1.4 Analysis of the Primary Efficacy Outcome**

72 The primary outcome of MH closure of the inner retinal layers without rescue treatment through
73 8 weeks is a binary variable that is graded by the central reading center. The proportion of eyes
74 meeting the primary outcome will be determined and the 95% Wilson (score) confidence interval
75 will be calculated.¹⁻³

76 Since the chance of re-opening after closure before 8 or 24 weeks is highly unlikely, an eye with
77 MH closure of the inner retinal layers without rescue treatment at any time prior to 24 weeks will
78 be considered to have met the outcome through 24 weeks if the participant is lost to follow-up.
79 Similarly, any eye receiving rescue treatment prior to 24 weeks will be considered not to have
80 met the outcome through 24 weeks.

81 Multiple imputation will be used to impute missing data for eyes lost to follow-up that did not
82 have prior MH closure or rescue treatment documented. The imputation model will include MH
83 status at 1, 4, 8, and 24 weeks.

84 A sensitivity analysis will be conducted using the same approach as above, but without multiple
85 imputation (i.e., complete-case analysis).

86 **1.5 Analysis of the Secondary and Exploratory Outcomes**

87 The ITT analysis cohort will be used for all secondary and exploratory outcomes.

88 **1.5.1 Secondary Efficacy Outcomes**

89 There are two time-to-event outcomes to be evaluated through 24 weeks: (1) macular hole
90 closure of the inner retinal layers without rescue treatment and (2) central VMT release without
91 rescue treatment. Each of these outcomes will be graded by the central reading center. For each
92 outcome, a Kaplan-Meier curve will be constructed and the cumulative probability of the
93 outcome with 95% confidence interval will be estimated for the final time point. Data from eyes
94 not observed to meet the outcome or that receive rescue treatment will be censored on the date of
95 their final visit (not the date of rescue treatment). The analysis of central VMT release without
96 rescue treatment will be limited to eyes with central VMT at baseline. Because the chance of re-

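### SAP 2.0 drops the combined central VMT and vitreopapillary traction release outcome after data review and plans no other report of it; a small sample supports dropping the adjustment, not the count

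*SAP*

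**What the plan says.** Protocol 8.4 includes among its secondary outcomes "Proportion of eyes with central VMT release and vitreopapillary traction release* without" rescue treatment through 24 weeks, as a time-to-event analysis. Protocol 8.7.1 says that this outcome and central VMT release alone are graded by "the central reading center and will be analyzed as above. The latter analysis will be adjusted for" vitreopapillary traction status at baseline. The latter analysis is the combined outcome. Protocol 8.7 sets the population: "The ITT analysis cohort will be used for all secondary and exploratory outcomes".

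SAP 2.0 changes this. Section 1.17 says of the combined outcome: "release without rescue treatment at 24 weeks has been removed from the list of" secondary outcomes, because the final sample was smaller than expected. The version table gives the background: "Revisions were made to accommodate a smaller than anticipated sample size after early stopping for safety concerns". It also gives the timing: "Changes were made following review of study data". SAP 1.5.1 now reads "There are two time-to-event outcomes to be evaluated through 24 weeks: (1) macular hole" closure without rescue and, second, central VMT release without rescue.

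The key secondary outcomes in the Protocol Summary are "proportion of eyes with central VMT release without rescue treatment, proportion of eyes with rescue treatment, mean change in visual acuity". The combined outcome is not among them.

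**The concern.** An outcome that is dropped once data have been seen, with no replacement, is a standard route to selective reporting, whatever the motive. Here the stated reason covers only part of the step. A small sample can make an adjusted analysis unworkable. It cannot make a count unworkable, and this study tests no hypothesis and has no power requirement to miss.

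The information at stake is narrow. In an eye without vitreopapillary traction at baseline, the combined outcome adds little to central VMT release, which is kept. What is lost concerns eyes with both tractions at baseline: this was the only listed outcome showing whether both released. Without a planned count of those eyes, the plan does not commit to showing how far small numbers explain the removal.

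**Working it through.** **1. Outcome lists side by side.** Protocol 8.4 has eight secondary outcomes: macular hole closure through 24 weeks, central VMT release, the combined release, mean acuity change, 10-letter gain, 10-letter loss, rescue before 8 weeks and rescue before 24 weeks. SAP 1.2.2 has the same list without the combined release, so 8 − 1 = 7. The 24-week time-to-event outcomes fall from 3 to 2.

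**2. Is it planned elsewhere?** It is not in the exploratory outcomes (SAP 1.2.3). The description-only tables in SAP 1.2.1 and 1.2.2 cover hole closure, central VMT release and rescue. SAP 1.5.1 analyses the two retained outcomes. Vitreopapillary traction is named in the SAP only in the 1.17 removal note. SAP 1.9 tabulates baseline characteristics without listing them, so baseline vitreopapillary traction status may or may not appear there.

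**3. Does the plan treat a small sample the same way elsewhere?** It does not.
- In the same list in SAP 1.17, epiretinal membrane is removed as a covariate. The outcomes whose imputation models used it (Protocol 8.6 and 8.7.1) stay in SAP 1.4 and 1.5.1. The parallel step here would be to drop the adjustment and keep the outcome.
- SAP 1.11 runs the primary epiretinal membrane subgroup analysis, a logistic regression with a P value, whatever the sample size.
- SAP 1.2 already uses description-only tables, and SAP 1.5.1 already limits central VMT release to eyes with that traction at baseline.

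**4. What small numbers do to precision.** The only sample size figures in the documents are in Protocol Table 1. The Wilson half-width is

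h = z·√[p(1−p)/n + z²/(4n²)] / (1 + z²/n), with z = 1.96.

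At n = 50 it gives 9.9, 12.3 and 13.4 points for p = 85%, 70% and 50%, as in the table. All nine cells of the table are reproduced.

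The documents give neither the final number of eyes nor the number with baseline vitreopapillary traction, and Protocol 2.2.2 requires only central adhesion. The sizes below are therefore assumptions, at p = 50%:
- n = 10: 1.96·√(0.0250 + 0.0096)/1.384 = 26.3 points
- n = 5: 1.96·√(0.0500 + 0.0384)/1.768 = 33.0 points

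Such an interval is wide, but it can be computed and reported.

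**5. Why no eye should leave the denominator.** Assume 10 eyes, 5 with both releases and 1 lost before both released. Leaving the lost eye out gives 5/9 = 55.6%. Counting it as not met gives 5/10 = 50.0%, and as met 6/10 = 60.0%. At this size one eye moves the figure by several points, so unknown status has to be shown as its own count.

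**The case against.** The strongest case on the other side is that little is lost. The removal, its timing and its reason are all stated in the SAP, and anyone who compares the two public documents will see them. The outcome is not a key secondary outcome, its central VMT component is still analysed, and the affected subset may be tiny. Half-widths of 26 to 33 points at assumed sizes even lend the sponsor's reason some support. No rule in the documents requires a removed outcome to be counted, so that is a judgement about good reporting. SAP 1.9 might also give the baseline number without any change.

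Most of this stands, and it limits the point to a modest one. It does not remove it: imprecision is a reason to describe without adjusting, and SAP 1.9 does not commit to the row.

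Three stronger readings are tempting, and the documents support none of them.
- A reader might infer that the outcome was dropped because its results were unfavourable. No results are given, and the stated reason is sample size.
- A reader might infer that it will certainly go unreported. The SAP does not say so; it only plans no report.
- A reader might infer a breach of Protocol 8.1, which has the SAP finalized before data are first reviewed. SAP 1.0 is dated 09 Oct 2019 and the date of first review is not given, so no breach can be shown.

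**Conclusion.** The point holds as a modest risk of selective outcome reporting. One of eight secondary outcomes, and one of three 24-week time-to-event outcomes, was removed after data review and left with no planned report. The reason given justifies losing the adjustment but not the count. These facts rest on the text alone.

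The consequence cannot be sized, because it depends on how many eyes had both tractions at baseline. If there were almost none, the outcome was uninformative, and a baseline count would show it. The precision figures above rest on assumed sizes and are illustrations only.

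**What to change.** In SAP 1.2.2, restore the outcome as a description-only tabulation without statistical comparison. In SAP 1.9, name vitreopapillary traction status among the baseline characteristics.

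Among all eyes with both central VMT and vitreopapillary traction at baseline, give the counts through 24 weeks of:
- both released without rescue, including eyes seen with both released and later lost, as SAP 1.5.1 treats central VMT release;
- rescued, counted as not met, also as in SAP 1.5.1;
- not both released, without rescue, at the 24-week visit;
- status unknown: lost before both had released (including eyes with only one released), or OCT ungradable.

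Keep all these eyes in the displayed total and drop none from the denominator. If an estimate is wanted, use the unadjusted Kaplan-Meier method that SAP 1.5.1 applies to the two retained outcomes.

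State in the results that the outcome was specified in the protocol, was removed from the secondary list after data review, and is shown descriptively without the planned adjustment.

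The cost is a few lines of SAP text, one small table and one or two sentences. The protocol already plans reading-center grading of the outcome and use of baseline status, so no new assessment should be needed if that grading was done as planned. The downside is that the counts may be very small and the tabulation is itself post hoc.
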